### **Design of the study:**

Open-label DCS (daily dose of 50 mg) for 8 weeks – Treatment Arm A, followed by four 6-week periods of double-blind DCS or placebo with one week of washout in between. Subjects will be randomized to DCS-placebo-DCS-placebo or to placebo-DCS-placebo-DCS by the McLean Hospital research pharmacist, [name]. These four double-blind exposures (two each for DCS and placebo) will be followed by a 6-week single-blind exposure to DCS (subjects and the person doing the clinical assessments will not know if they are getting DCS or placebo, but Drs. [name], [name], and [name] will know that they are getting DCS). After a one-week washout, this single-blind exposure will be followed by 6 weeks of open-label DCS. The length of each double-blind arm is limited to six weeks to minimize the length of symptom exacerbation experienced by the subjects when they are receiving placebo. The patients’ usual psychotropic drug regimen will not be altered as part of the study, but an attempt will be made to keep those medications unchanged throughout the study if possible. Both the DCS (source: The Chao Center) and the placebo will be dispensed by the McLean Hospital Pharmacy. Throughout the study, subjects will take one vitamin-B complex tablet per day.

[name] will be responsible for medical oversight of the d-cycloserine (DCS) augmentation component of the study. [name] will serve as his back-up. [name] will be responsible for medical oversight of the imaging components of the study.

Briefly describe study procedures. Include any local site restrictions, for example, “Subjects enrolled at Partners will not participate in the pharmacokinetic portion of the study.” Describe study endpoints.

Before beginning the study, subjects will have an EKG and physical exam performed by their personal physician. This will be repeated at week 8 and week 44 at the end of the study. Blood work will be done at the same time and consist of the following tests: comprehensive metabolic profile (CMP), lipid panel, GGT, uric acid, CBC with differential, CRP-hs. Blood will also be drawn for large and small amino acid levels and psychotropic drug levels.

Periodic blood tests and weight checks, clinical ratings (PANSS, Clinical Global Impression scale, Brief Psychiatric Rating Scale, Young Mania Rating Scale, HAM-D), side effect monitoring, movement disorder assessments (AIMS and SAS) and neurocognitive testing (MATRICS) – see schema for details.

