After the discontinuation period is completed, the subjects will receive open-label DCS (50 mg/d) for 8 weeks. Subjects will be formally evaluated on all of the clinical measures (see below and schema) every two weeks but will be in weekly phone contact with the PI throughout. Although we do not anticipate that DCS will cause a worsening of their symptoms, we cannot rule out this possibility in advance. If the BPRS shows an additional 25% worsening or severity of specific symptoms changes by two additional points (compared to their new baseline), that subject will be discontinued. [name] will review the clinical data before a subject is discontinued. . Subjects who complete the open label DCS trial will be randomized to DCS or placebo for 6-week periods in a double-blind design. The McLean Hospital research pharmacist, [name], will determine the randomization and will not be blind to drug or placebo condition, but the subjects and all other study staff will be. There will be a total of four 6-week double-blind exposures to DCS or placebo, each followed by one week of washout. A one-week washout is more than sufficient for both a behavioral and biochemical washout (half-life of DCS is 10 hours, so technically, two days should be sufficient). The two possible randomization schemas are: DCS-placebo-DCS-placebo or placebo-DCS-placebo-DCS, to be determined by the research pharmacist. We are limiting the length of each double-blind arm to six weeks to minimize the length of symptom exacerbation experienced by the subjects when they are receiving placebo. These four double-blind exposures (two each for DCS and placebo) will be followed by a 6-week single-blind exposure to DCS (subjects and the person doing the clinical assessments will not know if they are getting DCS or placebo, but Drs. [name], [name], and [name] will know that they are getting DCS). After a one-week washout, this single-blind exposure will

be followed by 6 weeks of open-label DCS. Subjects will be aware of the design and thus will know that if they experience a worsening of symptoms in any clinical arm, it will be time-limited.

II. Specific Aims

a. Objectives/hypotheses

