The subjects will also be given emergency contact numbers for Drs. [name], [name], [name], and [name]. The subjects will also be told to go the nearest emergency room if they experience any acute side effects (e.g., vomiting, diarrhea). [name], a consultant on this project, has a great deal of experience in using DCS to augment the therapeutic effects of antipsychotic medication and will be available to advise the study team about any needed changes (i.e., dose reduction, discontinuation) based on side effects or changes in clinical state. Decisions about how best to proceed will be made in consultation among Drs. [name], [name], ([name] if [name] is not available), [name], and the McLean pharmacist. Based on [name] extensive experience

using this dose of DCS, it is very unlikely that it will be necessary to discontinue the trial altogether. Should there be changes in any arm of the study, such as temporary discontinuation or extending the time period, the IRB will be notified. If subjects develop side effects that make them too uncomfortable or that make it medically necessary to discontinue the study, the study will be stopped. This level of oversight for subjects who are not local seems reasonable for monitoring subjects taking a compound that has been safely used as an augmentation strategy. The same procedures were used in the initial glycine augmentation study and the current extended glycine trial and have worked effectively.

The PI has talked all of the people involved in the study (Drs. [name], [name], [name], [name], [name], and [name]; [name]) about the adequacy of the plan to provide medical and/or psychiatric monitoring of these patients while they are taking a novel compound; they have agreed that the proposed plan is acceptable. [name] is the psychiatrist for one of the subjects and [name] is the psychiatrist for the other. Blood work results are faxed to them and they are kept apprised of any notable developments (e., beginning and end of any phase of the study, worsening of clinical state, improvement in clinical state). They, in turn, contact the PI if they become concerned about changes in clinical state or side effects.

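### The unblinded research pharmacist is included in decisions on treatment changes, with no exemption for double-blind arms B to E, so those decisions can be influenced by knowledge of treatment

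*SAP*

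**What the plan says.** **Who knows the treatment.** The design summary at the end of SAP section I says that the McLean Hospital research pharmacist "will determine the randomization and will not be blind to drug or placebo condition, but the subjects and all other study staff will be". It adds: "The two possible randomization schemas are: DCS-placebo-DCS-placebo or placebo-DCS-placebo-DCS, to be determined by the research pharmacist". The Protocol gives the task to the same role under its design heading: "Subjects will be randomized to DCS-placebo-DCS-placebo or to placebo-DCS-placebo-DCS by the McLean Hospital research pharmacist".

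**Who decides on changes.** SAP section IX (Monitoring and Quality Assurance) has a consultant available to "advise the study team about any needed changes (i.e., dose reduction, discontinuation) based on side effects or changes in clinical state". The next sentence says that decisions on "how best to proceed will be made in consultation among Drs. [name], [name], ([name] if [name] is not available), [name], and the McLean pharmacist". Shortly afterwards it adds: "Should there be changes in any arm of the study, such as temporary discontinuation or extending the time period, the IRB will be notified".

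**Other routes.** The BPRS discontinuation rule in SAP section I has one named person who "will review the clinical data before a subject is discontinued". The Protocol's suicidality procedure uses a conference call among named people. Neither mentions the pharmacist by role.

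**The concern.** The only person described as unblinded in arms B to E is also a party to the consultation on changing treatment in response to side effects or clinical state. Two things follow.

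- **The decision itself.** Whether a blinded period is changed or ended could depend on what the subject is taking. The SAP's analysis (section VI) is descriptive: magnitude of change, and correlations of change scores, on DCS versus placebo. With two subjects there is little other data to dilute the effect of one period altered with knowledge of treatment.
- **Disclosure.** The pharmacist's contribution could reveal the allocation to the physicians. In arm B the PI telephones the subjects weekly and a study physician calls at the end of weeks 10, 12 and 14. Arms C to E repeat this at corresponding times. If these people learn the treatment, later monitoring and escalation are no longer blind.

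The trigger is foreseeable. Both documents limit each double-blind arm to six weeks because they anticipate symptom exacerbation on placebo.

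**Working it through.** The plan gives no figure to reproduce. The check sets the statements side by side and then counts.

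**Step 1: do the two SAP sections conflict?**

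| Question | SAP section I | SAP section IX |
|---|---|---|
| Pharmacist's knowledge | Knows DCS or placebo | Not addressed |
| Other staff | Blind | Not addressed |
| Pharmacist's part in decisions on changes | Not mentioned | Included in the consultation |
| Arms covered | Double-blind arms | No exemption; the notification sentence refers to any arm |

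Together they place one participant who knows the treatment among others who are meant not to. The visible text does not confine the pharmacist to allocation-neutral input, set a code-break rule, or require a disclosure to be recorded. The plan can be explicit about who knows what: for single-blind arm F it lists the doctors who will know and says that the subjects and the assessor will not.

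**Step 2: what would one disclosure reveal?**

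| Sequence | Arm B | Arm C | Arm D | Arm E |
|---|---|---|---|---|
| 1 | DCS | placebo | DCS | placebo |
| 2 | placebo | DCS | placebo | DCS |

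The sequences differ in every arm, so learning the treatment in any one arm fixes the sequence and hence all 4 of 4 arms. If the two sequences are taken as equally likely (an assumption; the visible text gives no ratio), the chance of naming the treatment correctly rises from 1/2 to 1.

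**Step 3: how much double-blind time is then at risk?**

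Inputs: four double-blind arms of 6 weeks each, in weeks 10 to 36 with one-week washouts between them. Weeks at risk = 6 × number of double-blind arms still to run.

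| Disclosure at the start of | Arms left | Weeks at risk |
|---|---|---|
| B | 4 | 6 × 4 = 24 |
| C | 3 | 6 × 3 = 18 |
| D | 2 | 6 × 2 = 12 |
| E | 1 | 6 × 1 = 6 |

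These are upper limits for one subject, since a disclosure partway through an arm leaves less. They are not extended to the second subject, because the visible text does not say how the two subjects' sequences are related.

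**The case against.** The strongest reply is that consultation is not disclosure. SAP section I says that all other staff stay blind, and a pharmacist can advise without revealing the code. This stands: a reader might infer that decisions in the double-blind arms are in fact made with knowledge of treatment, but the visible text does not say that the allocation is shared or used. What it shows is that nothing prevents it.

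Further points, and what remains of each:

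- **Outcome rating is separate.** The Protocol has one named person performing all clinical assessments, and arm F shows that doctors can know the treatment while the assessor does not. So disclosure to the physicians does not by itself unblind the ratings. With names removed, one cannot check whether the assessor belongs to the deciding group. This limits the size of the problem but leaves the decisions themselves exposed.
- **Earlier data survive.** A reader might infer that one disclosure spoils all 24 double-blind weeks, or half of the trial's blinded evidence. It does not: learning the sequence later cannot unblind ratings already completed.
- **Placebo does not make disclosure likely.** A reader might infer that a dose reduction would expose a placebo arm. The same pharmacy compounds DCS and placebo as double-blind capsules, so a matched change could keep the blind. The Protocol also expects the dose to be well tolerated. The frequency of such consultations is unknown.
- **The scope is narrower than every change.** The any-arm sentence provides for IRB notification and names no decider; its link to the consultation comes from context. The BPRS and suicidality routes do not mention the pharmacist by role.
- **Text is missing.** Parts of both documents were removed before review, and a code-break procedure may stand there.

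**Conclusion.** The point holds as a conflict between two stated rules. SAP section I reserves knowledge of the allocation to the pharmacist, and SAP section IX brings the pharmacist into decisions about treatment changes without exempting the double-blind arms. Those decisions can be influenced by knowledge of treatment, and the discussion could disclose the allocation. A disclosure would put at risk that subject's remaining double-blind weeks, from at most 24 down to 6 according to the arm in which it occurs.

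This rests on two assumptions: that the McLean pharmacist of section IX is the research pharmacist of section I, which is very likely but not stated word for word; and that the removed text holds no rule that already separates the two roles. The documents do not establish that unblinded decisions will occur, how often, or that they would reach the person scoring outcomes. The correction is worth making because it is specific, removes an avoidable source of bias and costs little.

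**What to change.** Reconcile SAP sections I and IX with a short paragraph for arms B to E:

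- The blinded physicians and the consultant make the decision and record it. The pharmacist is left out, or gives only allocation-neutral input such as supply and general drug information.
- The pharmacist remains code holder and releases the allocation on a study physician's documented request when a subject's immediate care depends on it.
- Each release is logged with its date, arm and recipients.
- That subject's double-blind data after a release are flagged as unblinded in the analysis (SAP section VI). Ratings completed before it are kept as blind.

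The pharmacist's part in the open-label arms A and G and in single-blind arm F can stay as it is. If a code-break procedure already exists elsewhere, a cross-reference in section IX and a statement of the pharmacist's limited role would be enough.

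The cost is a few sentences, a release log and an analysis flag. Emergency access to the code is kept, and no dose or clinical criterion changes.
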